9 OVERALL STATISTICAL CONSIDERATIONS

9.1 Determination of Sample Size

9.1.1 Efficacy

The total number of participants planned to be enrolled is approximately 600 (300 per group). If the true control rate for progression to moderate or severe category or greater is at least 30%, 294 participants per group will result in 80% power when the true study intervention effect is 35% as a relative decrease of rate progression, i.e., a true rivaroxaban rate of progression of 19.5% is 35% lower than that of a true placebo-control rate of progression of 30%. This sample size accounts for a drop-out rate of 10% and a 1-sided Type I error rate of 2.5%. To account for one planned interim futility analysis without adversely affecting the statistical power, the sample size was increased to 300 per group.

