stratified Miettinen and Nurminen method [Miettinen, 1985] with the Cochran-Mantel-Haenszel (CMH) weights [Lu, 2008], stratified by number of days since onset of symptoms at time of randomization (<6 days or ≥6 days). The point estimates and variance estimated for each stratum j using the Miettinen and Nurminen method are defined as

$$\hat{d}_j = \hat{p}_{1j} - \hat{p}_{2j}$$

where \hat{p}_{1j} and \hat{p}_{2j} are the proportions of participants in rivaroxaban and placebo group who had progression of COVID-19 through Day 28, respectively, and

$$\widetilde{Var}_j(\delta) = \left(\frac{n_j}{n_j - 1}\right) \left(\frac{\tilde{p}_{1j}(\delta) (1 - \tilde{p}_{1j}(\delta))}{n_{1j}} + \frac{\tilde{p}_{2j}(\delta) (1 - \tilde{p}_{2j}(\delta))}{n_{2j}} \right)$$

where $n_j = n_{1j} + n_{2j}$, and $\tilde{p}_{1j}(\delta)$ and $\tilde{p}_{2j}(\delta)$ are the maximum likelihood estimates of rivaroxaban and placebo proportions under the restriction that the risk difference is δ . For the hypothesis specified, $\delta = 0$. The maximum likelihood estimates of p_{1j} and p_{2j} , subject to the constraint that the risk difference is δ , are computed as

$$\tilde{p}_{1j}(\delta) = 2u \cos(w) - b/3a \quad \text{and} \quad \tilde{p}_{2j}(\delta) = \tilde{p}_{1j}(\delta) + \delta$$

where

$$\begin{aligned} w &= (\pi + \cos^{-1}(v/u^3))/3 \\ u &= \text{sign}(v) \sqrt{b^2/(3a)^2 - c/3a} \\ v &= b^3/(3a)^3 - bc/6a^2 + d/2a \\ a &= 1 + \theta \\ b &= -(1 + \theta + \hat{p}_{1j} + \theta\hat{p}_{2j} + \delta(\theta + 2)) \\ c &= \delta^2 + \delta(2\hat{p}_{1j} + \theta + 1) + \hat{p}_{1j} + \theta\hat{p}_{2j} \\ d &= -\hat{p}_{1j}\delta(1 + \delta) \\ \theta &= n_{2j}/n_{1j} \end{aligned}$$

The CMH weights will be used to combine the point estimates and variance estimates that are calculated within each stratum using the Miettinen and Nurminen method.

$$\hat{d} = \sum_j w_j \hat{d}_j$$

$$\widetilde{Var}(\delta) = \sum_j w_j^2 \widetilde{Var}_j(\delta)$$

where CMH weights, w_j , are defined as

$$w_j = W_j / \sum_k W_k$$

where

$$W_j = \left(\frac{1}{n_{1j}} + \frac{1}{n_{2j}} \right)^{-1}$$

A score-based test statistic for the null hypothesis is that the risk difference equals δ can be expressed as

$$Z(\delta) = (\hat{d} - \delta) / \sqrt{\widehat{var}(\delta)}$$

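### The SAP's primary confidence-interval formula has a sign error: programmed as printed, the 95% interval is 19% too narrow at the design effect and covers 88.6%

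*SAP*

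**What the plan says.** The primary estimate of effect is the absolute risk difference in progression through Day 28, with a stratified Miettinen-Nurminen 95% interval and CMH weights (SAP 11.1.1).

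- **Arm labels.** The two observed proportions "are the proportions of participants in rivaroxaban and placebo group who had progression of COVID-19 through Day 28, respectively". Arm 1 is therefore rivaroxaban and arm 2 placebo, and the stratum difference is written as p1 minus p2.
- **Restriction.** The tilde quantities "are the maximum likelihood estimates of rivaroxaban and placebo proportions under the restriction that the risk difference is" δ.
- **Restricted placebo estimate.** "p}_{2j}(\delta) = \tilde{p}_{1j}(\delta) + \delta".
- **Statistic and interval.** Z(δ) is (d-hat − δ) divided by the root of the restricted variance. The limits are the δ values at which Z equals +1.96 and −1.96. The hypothesis test sets δ to 0.

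The same method is carried to disease resolution (SAP 11.2.3), to progression at earlier days (SAP 11.2.4), and to the mITT and PP repeats of the primary analysis (SAP 11.1.2).

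**The concern.** If the risk difference is p1 − p2 and is held at δ, then p2 must equal p1 − δ. The printed line adds δ instead, so the placebo estimate is wrong by 2δ. At δ = 0 this does no harm. A confidence limit, however, is normally found at a non-zero δ, and the variance used there would be wrong.

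The trial stopped after crossing its futility boundary (SAP section 4). What remains to be reported is largely how much benefit or harm the data exclude, and that is read from this interval. The SAP is also the specification for independent programming: someone following it literally would either reproduce the error or meet an unexplained mismatch with a standard routine.

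**Working it through.** **Inputs.** SAP 9.1.1 gives the rates: "a true rivaroxaban rate of progression of 19.5% is 35% lower than that of a true placebo-control rate of progression of 30"%. It also gives "294 participants per group will result in 80% power when the true study intervention effect is 35% as a relative decrease", raised to 300, and "This sample size accounts for a drop-out rate of 10% and a 1-sided Type I error rate of 2.5"%. The formulae are those of SAP 11.1.1.

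**1. The plan's own sample size.** With pooled rate 0.2475:

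n = [1.960·√(2·0.2475·0.7525) + 0.8416·√(0.30·0.70 + 0.195·0.805)]² / 0.105² = 264 per arm.

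Then 264/0.9 = 293.3, so 294. This matches the SAP.

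**2. Which restriction do the printed coefficients solve?** Take 19.5% vs 30%, 300 per arm (θ = 1), δ = −0.17:

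- a = 2; b = −(1 + 1 + 0.195 + 0.30 − 0.17·3) = −1.985
- c = 0.0289 − 0.17·2.39 + 0.495 = 0.1176; d = 0.195·0.17·0.83 = 0.02751
- v = −0.01960, u = −0.29975, w = 1.2990
- p1 = 2u·cos(w) − b/(3a) = −0.1609 + 0.3308 = 0.1699

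Compare the printed p1 with a direct numerical maximisation of the binomial likelihood under each restriction:

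| δ | Printed p1 | Direct fit, p1 − p2 = δ | Direct fit, p2 = p1 + δ |
|---|---|---|---|
| −0.17 | 0.1699 | 0.1699 | 0.3599 |
| −0.105 | 0.1950 | 0.1950 | 0.3138 |
| −0.03 | 0.2310 | 0.2310 | 0.2652 |
| +0.05 | 0.2776 | 0.2776 | 0.2206 |

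The coefficients solve p1 − p2 = δ. Only the p2 line departs from that convention, so relabelling the arms does not rescue it. At δ = −0.17 the right p2 is 0.340; the printed line gives −0.0001.

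**3. Variance at the design effect (δ = −0.105).** p1 = 0.195.

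- Correct, p2 = 0.300: (600/599)·(0.195·0.805 + 0.300·0.700)/300 = 0.001225, SE 0.0350
- Printed, p2 = 0.090: (600/599)·(0.195·0.805 + 0.090·0.910)/300 = 0.000798, SE 0.0282

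**4. Coverage.** The interval contains the true δ when |Z(δ)| ≤ 1.96. The SE ratio is 0.807, so the effective cut-off is about 1.96·0.807 = 1.58, which gives roughly 88.6%. Binomial enumeration at 300 per arm gives 88.6% as printed and 95.0% corrected. At 270 per arm (300 less 10%) it gives 88.5% and 95.0%. At true rates of 13% vs 20%, coverage as printed is 87.5%.

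**5. Limits.** At the printed lower limit, δ = −0.1516, p1 = 0.1765, p2 = 0.0248 and SE = 0.0238, so Z = 0.0466/0.0238 = 1.96. The correct lower limit is δ = −0.1735, with p2 = 0.342 and SE 0.0349. Single-stratum results, in percentage points:

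| Rivaroxaban vs placebo, n per arm | Correct 95% CI | As printed | Width change |
|---|---|---|---|
| 19.5% vs 30%, 300 | −17.35 to −3.61 | −15.16 to −4.04 | −19.0% |
| 19.5% vs 30%, 270 | −17.72 to −3.23 | −15.37 to −3.64 | −19.0% |
| 19.5% vs 30%, 100 | −22.36 to 1.51 | −17.62 to 1.79 | −18.7% |
| 13% vs 20%, 300 | −12.98 to −1.07 | −10.77 to −1.26 | −20.2% |
| 30% vs 30%, 300 | −7.33 to 7.33 | −6.76 to 7.75 | −1.0% |
| 35% vs 30%, 300 | −2.50 to 12.46 | −2.35 to 12.91 | +2.0% |
| 19.5% vs 15%, 300 | −1.56 to 10.59 | −1.37 to 11.78 | +8.1% |

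Two strata with CMH weights (150 + 150 or 200 + 100 per arm) at the design rates also give −19.0%.

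**6. Test at δ = 0.** Z = −2.977 at the design rates under either sign.

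**The case against.** The strongest reply is that the 19% belongs to a benefit this trial is unlikely to show. The SAP version under review postdates the futility stop, and the example boundary in SAP 11.5.1 is a one-sided p of 0.755, about 0.69 standard errors in the direction of harm. With assumed values of 250 per arm and 20% on placebo (the documents do not give the final n), rivaroxaban rates of 20%, 22% and 25% give width ratios of 0.99, 1.02 and 1.05, and coverage of 95.0%, 95.7% and 96.4%. Each limit moves by about 0.3 to 1.1 points. This stands. Near no effect or harm the error is a shift, not a narrowing. The shift still matters for a futility result: in all three cases the printed lower limit excludes some benefit that the correct interval keeps (at 20% vs 20%, −6.11 instead of −7.06).

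Other points that stand:

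- The primary p-value and the futility statistic do not change.
- At the design rates with 300 per arm, p2 at the printed formula's own lower limit is +0.025. The negative value at δ = −0.17 lies outside that interval. With 100 per arm, p2 is −0.008 at the printed limit itself.
- For disease resolution the loss is smaller: width ratio 0.95 at an assumed 60% vs 50%, and 0.90 at 70% vs 60%. Hospitalisation uses CMH risk ratios and is untouched.
- The method is named, referenced and correctly described in words, so a standard routine may well be right. Appendix 4 (SAS Code) shows no code in the text available, so this cannot be checked.
- The point rests on one operator in a machine-read equation, and a misreading of that sign cannot be wholly excluded.

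These limit the likely consequence. They do not make the printed line consistent with the rest of its section.

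**Conclusion.** The concern holds. The printed restricted placebo estimate contradicts the SAP's own difference, coefficients and test statistic. If programmed literally, it makes the 95% interval 19% too narrow at the design effect (coverage 88.6%), shifts it upward by about half a point at each limit when both arms are 30%, and widens it by 2% to 8% in the two harm cases tabulated. It can also return a negative probability, for example at the printed lower limit with 100 per arm. Hypothesis testing and the futility decision are not affected.

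These sizes assume the line is coded as printed and that its sign was read correctly from the PDF. The sign error itself does not depend on any assumed event rate.

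**What to change.** In SAP 11.1.1, change the line to p2j(δ) = p1j(δ) − δ. Before the final run, confirm that the analysis code holds p1 − p2 at δ and agrees with a direct maximisation of the restricted likelihood. Two single-stratum checks with whole-number counts separate the signs:

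- 39/300 vs 60/300 should give −12.98 to −1.07 points; the printed formula gives −10.77 to −1.26.
- 90/300 vs 90/300 should give a symmetric ±7.33; the printed formula gives −6.76 to +7.75.

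Apply the same confirmation to the outputs of SAP 11.1.2, 11.2.3 and 11.2.4. The cost is one character in the SAP and one programming check, with no change to data, design or hypotheses.

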11.1.2 Sensitivity Analyses

To assess the robustness of the primary results, analyses will be repeated for the primary analysis using the mITT and PP populations.

Sensitivity analysis will be performed according to their derived actual strata instead of the randomized strata.

In case any participants use any prohibited concomitant use of medication prior to treatment discontinuation and day 28, they will be flagged as significant protocol deviations and excluded from the per-protocol efficacy analyses.

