Autopsies of patients who died of COVID-19 revealed PE and DVT (including in people not suspected to have DVT before death). Histomorphological findings were distinctive vascular features with severe endothelial injury, and diffuse alveolar capillary microthrombi that was 9 times more prevalent in patients who died from COVID-19 than influenza [Ackermann 2020, Wichmann 2003]. Microthrombi in the pulmonary vasculature may explain the rapid deterioration and pulmonary collapse observed in patients who suddenly progress to acute respiratory distress syndrome.

Hospitalized patients acutely ill from medical conditions such as infections and pneumonia are at increased risk of VTE, for whom anticoagulant could be indicated. Risk assessment modeling studies are reporting 40% VTE risk among hospitalized COVID-19 patients [Wang 2020]. The World Health Organization (WHO) interim guidance recommends in-hospital prophylactic daily low-molecular weight heparin or twice daily subcutaneous unfractionated heparin [WHO(c) 2020]. Use of DOACs like rivaroxaban in the hospitalized population is limited by drug interactions with antiviral and other agents for treatment of COVID-19 or its complications. However, rivaroxaban may benefit high risk people with non-severe disease in the outpatient setting who are less likely to need those treatments with significant drug interaction with rivaroxaban.

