#### **6.10.1. Prohibited Medications**

**Table 5: Rivaroxaban prohibited medications/foods/supplements**

Drug Class	Examples (based on human in vivo data)	Known or Probable Effect
Anticoagulants	warfarin sodium (Coumadin®, Jantoven®), any medicine that contains heparin, including low molecular weight heparins, apixaban, Pradaxa [dabigatran], Savaysa [edoxaban], Bevyxxa [betrixaban], non-study Xarelto [rivaroxaban]	Increased risk of bleeding
Combined P-gp inhibitors and strong CYP3A4 inhibitors	cobicistat, conivaptan, indinavir, itraconazole, ketoconazole, posaconazole, ritonavir, saquinavir, telaprevir, telithromycin	Significant increase in rivaroxaban concentration
Combined P-gp inhibitors and moderate CYP3A4 inhibitors OR strong CYP3A4 inhibitors alone	amiodarone, azithromycin, clarithromycin, cyclosporine, diltiazem, dronedarone, erythromycin, fluconazole, grapefruit, lapatinib, mifepristone, nefazodone, nicardipine, ranolazine, tamoxifen, ticagrelor, verapamil, voriconazole	Moderate increase in rivaroxaban concentration in patients with normal renal function. Significant increase in rivaroxaban concentrations in patients with renal impairment
Combined P-gp inducers and strong CYP3A4 inducers	carbamazepine, dexamethasone, rifampin, St John's wort	Significant reduction in rivaroxaban concentration

Drug Class	Examples (based on human in vivo data  )	Known or Probable Effect
Inducers of P-gp	tipranavir	Effect may persist for several weeks following discontinuation of strong inducers of P-gp and/or CYP3A4 Significant reduction in rivaroxaban concentration Effect may persist for several weeks following discontinuation of strong inducers of P-gp and/or CYP3A4
Strong inducers of CYP3A4	bosentan, efavirenz, etravirine, fosphenytoin, naftillin, nevirapine, phenobarbital, phenytoin, primidone, rifabutin, rifapentine	Significant reduction in rivaroxaban concentration Effect may persist for several weeks following discontinuation of strong inducers of P-gp and/or CYP3A4

Modified from [UW 2020]

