### **6.11. Hospitalization**

If a participant clinically worsens, such as requiring hospitalization, it is expected that standard clinical care will be provided. Hospitalized participants may continue to receive study intervention if maintained on the originally randomized study-intervention regimen.

Accommodations will be made to facilitate these encounters within this specific setting. Clinical outcomes in hospitalized participants will be confirmed through the electronic health record, if possible.

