11.1 Primary Analysis

11.1.1 Estimand

The treatment policy estimand with respect to the primary efficacy objective is defined by the following:

Population: Participants in the ITT population.

Patient-level outcome: Binary outcome of progression to moderate or severe disease category or higher (Gates MRI ordinal scale ≥ 3) at any day through Day 28.

Intercurrent events: The following intercurrent events to be taken into account:

1. If a death occurs on or prior to Day 28, the participant will be considered as having progression to moderate or severe category (Gates MRI ordinal scale ≥ 3) through Day 28.
2. If hospitalization occurs on or prior to Day 28, the participant will be considered as having progression to moderate or severe category (Gates MRI ordinal scale ≥ 3) through Day 28.
3. If a participant is lost to follow-up on or prior to Day 28, the last observed Gates MRI ordinal scale status evaluation will be carried forward onward to Day 28.
4. If a participant discontinues the study prior to initiation of IP dosing on Day 1 (for any reason: lost to follow-up, progression to moderate or severe COVID-19, withdrawal of consent) and no Gates MRI ordinal scale assessment is available, the participant will be considered as having progression to moderate or severe category (Gates MRI ordinal scale ≥ 3) through Day 28.

Participants who discontinue study intervention will be followed at least until end of study, Day 35.

Population-level summary measure: Proportion of participants who progress to moderate or severe disease category or higher (Gates MRI ordinal scale ≥ 3) at any day through Day 28.

The primary efficacy analysis will be conducted in the ITT population. Participants randomized to rivaroxaban will be compared to participants randomized to placebo. For the primary efficacy analysis, the following primary hypothesis will be tested: Prophylactic treatment with rivaroxaban will reduce progression to moderate or severe disease category or greater (Gates MRI ordinal scale ≥ 3) relative to placebo in high risk participants with mild COVID-19.

The proportion of participants who have progression of COVID-19 at any time up to and including Day 28 and the corresponding 2-sided 95% CI, computed using the Mid-p method, will be summarized for the study intervention and control. The absolute difference in the risk of progression of COVID-19 and the corresponding 2-sided 95% CI will be assessed using the

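### The per-protocol rule on prohibited medication ignores whether use began after the primary event, so it can drop a participant together with the event

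*SAP*

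**What the plan says.** For robustness, SAP 11.1.2 states that "analyses will be repeated for the primary analysis using the mITT and PP populations". It then turns to participants who "use any prohibited concomitant use of medication prior to treatment discontinuation and day 28" and says "they will be flagged as significant protocol deviations and excluded from the per-protocol efficacy analyses". The window is set by treatment discontinuation and Day 28. The date of progression is not part of it.

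Several other passages bear on who falls under this rule:

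- Protocol Table 5 prohibits "any medicine that contains heparin, including low molecular weight heparins".
- Protocol 3.1.3 reports that WHO "interim guidance recommends in-hospital prophylactic daily low-molecular weight heparin or twice daily subcutaneous unfractionated heparin".
- Protocol 6.11 says "Hospitalized participants may continue to receive study intervention if maintained on the originally randomized study-intervention regimen".
- Protocol 6.10 requires study drug to be stopped if a prohibited medicine is indicated, and 7.1 lists this among the reasons for discontinuation.
- SAP 11.1.1 counts hospitalisation or death by Day 28 as progression. It also says: "The primary efficacy analysis will be conducted in the ITT population".
- SAP Table 2 defines the PP population by treatment taken as planned, mild disease at entry and no substantial deviation.

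**The concern.** A PP exclusion should remove people whose departure from protocol could have altered the outcome. Prohibited use that starts after the first primary event cannot do that, because the endpoint is binary through Day 28 and is already fixed. In this trial such use can be a consequence of the event: progression leads to admission, and admission leads to heparin. If exclusion follows, it depends on the outcome.

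The PP analysis could then show lower event rates and a smaller risk difference for reasons unrelated to adherence. It could also show a spurious difference if the arms differ in how often inpatient heparin overlaps with study drug. This matters somewhat more because SAP Version 2.0 removed three earlier sensitivity analyses of the primary endpoint. That leaves mITT, PP and derived strata in 11.1.2. The exclusion also covers the PP repeats of the secondary analyses (SAP 11.2), which include incidence of hospitalisation.

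**Working it through.** **Reading the rule.** There are three situations in which a participant progresses, is admitted and is given heparin:

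1. *Study drug stopped first, heparin afterwards.* Use is not before discontinuation, so the rule does not exclude. This is the course that Protocol 6.10 prescribes.
2. *Heparin started while tablets continue, or before they are stopped.* Use is before discontinuation, so the participant is excluded with the event.
3. *Tablets completed at Day 21, then progression and heparin on Days 22 to 28.* The SAP does not say whether completing treatment counts as discontinuation. If it does not, the participant is excluded with the event.

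A start of heparin and a stop of tablets on the same day is not resolved by the text.

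Two further routes could remove the same participants. Stopping tablets for heparin might be read as failing the treatment-as-planned criterion in SAP Table 2. And SAP Appendix 2 sets a medication start date with a missing day to the treatment date when month and year match, and a wholly missing one to the day before. If imputed dates feed the PP flag, heparin given after the event would appear to start before it.

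**Design figure (SAP 9.1.1).** Inputs: 30% vs 19.5%, one-sided 2.5%, 80% power, 10% drop-out. The mean rate is 0.2475.

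n = [1.960·√(2·0.2475·0.7525) + 0.8416·√(0.30·0.70 + 0.195·0.805)]² / 0.105² = 264 per group

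264/0.9 = 293.3, rounded up to 294. This matches the plan.

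**Effect of removing events.** Let f be the share of events excluded in an arm with true rate p. Removal takes the participant out of both numerator and denominator:

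PP rate = p(1 − f) / (1 − p·f)

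The documents do not give f, so the values below are assumptions. For f = 10%: placebo 0.27/0.97 = 27.8%, rivaroxaban 0.1755/0.9805 = 17.9%. Power uses 300 × 0.9 = 270 evaluable per group before exclusions.

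| f, both arms | Placebo | Rivaroxaban | Difference (points) | Risk ratio | Power |
|---|---|---|---|---|---|
| 0 | 30.0% | 19.5% | 10.5 | 0.65 | 81% |
| 10% | 27.8% | 17.9% | 9.9 | 0.643 | 78% |
| 25% | 24.3% | 15.4% | 8.9 | 0.632 | 72% |
| 50% | 17.6% | 10.8% | 6.8 | 0.612 | 57% |

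**Unequal removal with no true effect (30% in both arms).** Removing 25% of placebo events and 10% of rivaroxaban events gives 24.3% vs 27.8%: rivaroxaban looks 3.5 points worse (risk ratio 1.14). Reversing the shares makes it look 3.5 points better (risk ratio 0.87).

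**The case against.** The strongest reply is that the rule, read with Protocol 6.10, targets concurrent use. Concurrent use is a genuine breach, and participants whose tablets were stopped first are spared. If sites follow 6.10 and dates are complete, f from this rule is about zero. Protocol 6.11 lets inpatients stay on study drug but does not itself permit study drug together with heparin. The ordinal scale can also reach 3 on shortness of breath or respiratory rate alone, without admission. All of this stands. It limits the size, and nothing in the documents supports the upper values of f. It does not cure the rule, because 6.10 governs conduct while the SAP must classify what actually happened, including overlap and use after Day 21.

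A reader might infer more than the documents support:

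- *That every user of a prohibited medicine is dropped.* The rule stops at treatment discontinuation.
- *That stopping tablets on the day heparin starts leads to exclusion.* The SAP says prior to discontinuation; the same-day case is open.
- *That dexamethasone adds to the problem.* Table 5 lists it ("carbamazepine, dexamethasone, rifampin") as an inducer, but no passage says it is given for progression. The point rests on heparin.
- *That the trial's main result is biased.* The primary analysis is ITT, the mITT definition carries no prohibited-medication exclusion, the interim analysis used ITT, and no stated decision depends on PP.

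It is also fair to note that equal removal moves the risk ratio slightly away from 1, not towards it. The shrinkage is in the risk difference, which is the planned measure.

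**Conclusion.** The point holds in limited form. As written, the PP rule can exclude a participant because of the primary event and lose the event with them. That is a flaw in a stated rule, not just a missing detail.

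The documents do not allow the size to be estimated. It may be near zero if study drug is reliably stopped before heparin begins. Under equal removal of 10 to 50% of events the risk difference would fall from 10.5 to between 9.9 and 6.8 points, with little change in the risk ratio. Unequal removal of 25% and 10% would create a false difference of 3.5 points in either direction.

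These figures assume the design rates. The power column also assumes the planned numbers, and the trial stopped early, so it is illustrative only. The effect is confined to the PP sensitivity analyses.

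**What to change.** In SAP 11.1.2, for the PP analysis of the primary endpoint:

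- Exclude for prohibited medication only when the first use starts before the first primary event, meaning the earliest of a score of 3 or higher on the ordinal scale of Protocol Table 7, hospitalisation, or death. Keep participants whose use starts on or after that date, with the event counted.
- Apply the same timing to the treatment-as-planned criterion in SAP Table 2, so that stopping tablets because of the event does not exclude the participant by another route.
- Do not use start dates imputed under Appendix 2 to class use as pre-event.

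This timing also settles, for anyone with an event, the same-day case and use on Days 22 to 28.

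The cost is a few lines of SAP text and a change to the derivation of the PP flag. Concomitant medication and clinical status are already recorded at every visit through Day 28, and days of hospitalisation are an endpoint, so no new data collection should be needed. No clinical rule changes.
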